2.2.3 Retrospective cohort study in patients with suspected recurrent VTE

Finally, we examined potential predictors of recurrence by performing a post-hoc analysis of the REVERSE I study²⁶). Each patient in the REVERSE I cohort that had a suspected recurrent VTE during follow-up were screened for eligibility in the post-hoc analysis. Only patients with a first adjudicated suspected recurrent event were included. Potential clinical predictors of recurrent VTE consisted of clinical predictors collected at the baseline visit, information collected in physicians' clinical notes, and laboratory or imaging results at the time of the suspected recurrent VTE. The predictive value of each predictor was determined by the Chi-square test for nominal data and the unpaired 2-tailed T-test for continuous data.

In the REVERSE I cohort, out of the 646 patients who were followed, 402 patients had a suspected recurrent VTE within a mean of 20.2 months (range: 0 – 97 months) of follow-up. Of these, 376 patients were eligible for our study: 52.7% of patients were males, and the mean age was 53.1 years (\pm 17.5). Among all suspected recurrent VTE events, male gender and a positive D-dimer result at the time of suspected recurrent VTE ($p < 0.01$), as well as symptoms occurring for 10 days or less at the time of presentation ($p < 0.05$) were in favor of a recurrent VTE diagnosis. In addition, mean age was higher in patients with a confirmed recurrent VTE ($p < 0.05$). Patients who had a previous DVT confirmed were at higher risk of having a recurrence confirmed at their next suspected event than when the previous event was a proven PE ($p < 0.05$).

This is the first study to show that predictors for the diagnosis of a recurrent VTE may be different than predictors for the diagnosis of a first VTE. For instance, our results show that male gender is not only a risk factor for recurrent VTE²⁷, but is also an important predictor for confirmed VTE among patients with suspected recurrent VTE. None of the existing CDRs take gender into consideration. The main limitation of this analysis is that clinical information at the time of the suspected recurrence was extracted from patients' charts, and therefore is subject to bias, as the amount of clinical data in the case report form was limited. Nevertheless, the findings of this post-hoc analysis, along with the survey and literature review, support the need for a modified CDR specific to patients with a history of VTE. Improved diagnostic

management in this population would lead to more optimal clinical management and improved safety for these patients.

1. STUDY OBJECTIVES

1.1 Primary Objective

To assess the accuracy and usefulness of the Wells DVT, Wells PE and Geneva clinical decision rules (CDR) in patients with a clinically suspected recurrent Venous Thromboembolism (VTE).

1.2 Secondary Objectives

- To assess the utility of recalibrating the existing clinical decision rules.
- To derive a new CDR, specific to patients with a suspected recurrent VTE, and to assess whether this CDR would improve risk stratification as compared with existing CDRs.
- To assess the accuracy of D-dimer testing in patients with suspected recurrent VTE both on and off anticoagulation.
- To evaluate the accuracy of current CDRs in patients on anticoagulant therapy at the time of suspected recurrent VTE.

3. STUDY DESIGN

This is a multicentre, observational cohort study to prospectively identify potential predictors of recurrent VTE. The cohort consists of outpatients in the Thrombosis Clinic that are evaluated for suspected recurrent DVT and/or PE. Diagnostic management of suspected recurrent VTE will be according to usual clinical practice; therefore all patients with suspected recurrent VTE will receive a diagnostic work-up as per local standards of care. All consecutive eligible patients will be approached for enrolment into this study. A total of 745 participants will be enrolled at Canadian sites.

3.1 Patient Safety

This observational study poses minimal risk to participants. The study procedure consists of some additional questions and one follow-up call if the diagnosis is excluded. The risks associated with venipuncture (discomfort or bruising) are disclosed in the consent form. As per usual clinical care, all patients will be instructed on signs and symptoms of DVT and PE and advised to return to the hospital in case of any suspicion of a DVT or PE. As this is an observational study, adverse events will not be collected.

4. SELECTION AND ENROLLMENT OF PARTICIPANTS

This study will be conducted at Canadian sites. Consecutive outpatients presenting to the Thrombosis Clinics of the participating hospitals with signs or symptoms suggestive of recurrent VTE will be screened for eligibility.

4.1 Eligibility

Eligibility status of all participants must be confirmed by the local investigator or designate before enrolment. It is important that no exceptions be made to the eligibility criteria. Questions related to the eligibility requirements or specific criteria must be discussed with the coordinating centre before enrolment.

4.2 Inclusion Criteria

Participants must meet all of the inclusion criteria to participate in this study.

- 1) Outpatient with clinically suspected acute recurrent DVT or PE regardless of whether the previous event was a DVT or PE
- 2) Age ≥ 18 years old
- 3) Willing and able to give informed consent

4.3 Exclusion Criteria

Participants who meet one or more of the exclusion criteria at baseline screening will be excluded from study participation.

- 1) Life expectancy less than 3 months
- 2) Suspicion of upper extremity thrombosis or thrombosis at an unusual site (e.g. cerebral or abdominal venous thrombosis)
- 3) Previous VTE was distal DVT or subsegmental PE or at an unusual site
- 4) Suspected recurrent VTE is asymptomatic
- 5) Previously enrolled in this study

4.3.1 Rationale for Exclusion Criteria

1) precludes complete follow-up; 2) and 3) there are uncertainties surrounding the characteristics, diagnostic management, treatment and prognosis of these entities. Inter-observer agreement in imaging interpretation is lower, the risk of recurrent VTE appears to be much lower, and patients' management remains very heterogeneous; 4) uncertainties surrounding the clinical relevance of these findings; 5) prevents duplication of study data.

6. STUDY PROCEDURES

[figure not shown]

Figure 1: Study Flow

6.1 Screening and Consenting

Potentially eligible patients will be identified by a healthcare professional according to institutional policy on privacy. The investigator or delegate will obtain written informed consent from the patient before collecting any data or performing any study-related procedures.

Patients who meet the inclusion criterion, but who are excluded due to an exclusion criterion or who do not provide written consent will be recorded on a screening log.

6.2 Baseline Assessments and Diagnostic Management

6.2.1 Clinical examination and data collection

Once a patient has consented to participate, an investigator or attending physician will complete an assessment of suspected clinical predictors of recurrent VTE and will calculate the participant's clinical pretest probability using the existing CDRs. The diagnostic work-up of each participant will be handled in line with the current standard of care at the discretion of the treating physician. (For reference of the current standard practices, refer to **Appendix C: Flow Chart of Suggested Diagnostic Approach for Assessing Suspected Recurrent VTEs**)

Data collection of clinical predictors will be completed by the investigator or delegate, by way of participant interview, reviewing medical records, and physical examination. (For a complete list of clinical predictors, refer to **Appendix D: Collection of Clinical Predictors for Suspected Recurrent VTE**). Clinical notes and results of all diagnostic tests for suspicion of VTE, as well as the diagnostic conclusion and therapeutic management will be recorded for all patients.

6.2.2 D-dimer testing

All study patients will have a blood sample drawn at the time of suspected recurrence and frozen for central D-dimer testing. Serum samples will also be stored for future potential predictor assessment (other D-dimer assays or other biomarkers). Samples will be shipped in batches to the coordinating site and D-dimer levels will be determined in all patients using a single commercial assay (VIDAS D-dimer Exclusion II, bioMérieux Inc, Durham, NC). Please refer to the resource manual for details on processing, storage and shipping of D-dimer samples.

6.2.3 Imaging

All imaging results will be recorded and kept in the patient's study folder. Confirmed recurrent VTE will be treated according to the standard of care at the local institution by the primary physician.

Suspected DVT

Current practice for patients with suspected recurrent DVT is to receive a compression ultrasound (CUS) of the symptomatic leg to confirm or exclude the diagnosis. CUS will assess venous compressibility of the proximal veins from the common femoral vein down to and including the calf vein trifurcation.

Suspected PE

Suspected recurrent PE is most commonly investigated by CT pulmonary angiogram (CTPA) and confirmed by an intraluminal filling defect in a subsegmental or greater pulmonary artery. Alternatively, a ventilation-perfusion (V/Q) lung scan will assess for a "high probability" perfusion defect.

6.3 Follow-up Visits

All patients in whom a recurrent VTE is ruled out will receive a follow-up call at 3 months (90 ± 7 days) after the initial evaluation using a structured interview script. Research coordinators will be trained by the investigator or multicenter coordinator prior to follow-up to ensure consistency in eliciting new signs and symptoms of DVT and PE between sites. Any new leg or chest symptoms reported to study personnel during study follow-up will prompt clinical and diagnostic assessment. Participants with suspected VTE will be assessed in the Thrombosis Clinic (or Emergency Department) and ordered diagnostic testing as judged necessary by their physician or the investigator. If participants report that they sought medical attention for complaints of possible VTE, medical records and imaging results will be collected to prepare an adjudication report. Any participant who seeks medical attention during their follow-up period and is once again not diagnosed with a recurrent VTE will have an additional call at 90 (± 7 days) days after they were last assessed.

All deaths during follow-up will prompt chart review and all available information including interviews with next of kin will be documented to permit preparation of an adjudication report to determine if the death is PE related.

The follow-up period is relatively short and therefore participant loss to follow-up should be minimal. However, for participants that cannot be reached by phone, an exhaustive search will determine if outcome events have occurred (including calls to next of kin or pre-identified contacts, obituary searches, retrieval of death certificates, review local hospital databases) prior to participants being declared lost to follow-up.

9. STATISTICAL CONSIDERATIONS

9.2 Sample Size Calculation

Beyond our primary objective of validating existing CDRs, we aim at enrolling enough participants to allow the derivation of a new CDR specific to patients with suspected recurrent VTE, in order to assess whether such a new CDR could improve risk stratification in this patient population. As per accepted methodological criteria for the development of CDRs, 5-10 patients per predictor studied are required in the smallest outcome category.²⁹ At this point, we don't know if we will be able to derive a single CDR for recurrent VTE or if deriving two separate CDRs for DVT and PE will be more useful. Our sample size estimation takes this uncertainty into account. We would like to be able to use up to 10 predictors for patients with suspected DVT with a history of VTE and separately up to 10 predictors for patients with suspected PE with a history of VTE; this means that the required study sample is 100 participants with a confirmed recurrent DVT and 100 participants with confirmed recurrent PE.

In a study by [name] et al. for the diagnostic management of recurrent VTE, 26.6% of participants with suspected VTE had the diagnosis confirmed.¹¹ In another paper 40.3% of the participants with suspected PE with a history of VTE had their diagnosis confirmed.⁴ In the retrospective study that we performed as preparation for this prospective study, 29% of the participants with a suspected recurrent DVT had their recurrence confirmed and 25% of the participants with a suspected recurrent PE had the diagnosis confirmed.

For DVT, in order to be conservative, we used the percentage from our retrospective study, that is, 29%. That means that we need to enroll 345 participants with suspected recurrent DVT to have 100 participants with a confirmed recurrent DVT. For PE, using an estimate of a 25% confirmation rate we need 400 participants with a suspected recurrence to have 100 participants with confirmed PE. Total sample size for the study is estimated at 745.

If we consider that 15% of the potentially eligible participants approached for this study will be found to be ineligible or will not consent for this study, we need to screen 397 patients with a suspected recurrent DVT and 460 patients with a suspected recurrent PE for this study. Hence, to meet our total sample size of 745 we will need to screen approximately 857 for eligibility.

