9.6 Secondary Outcome Analysis

9.5.1 Recalibration / minor adjustment to existing rules

Recalibration

For each existing CDR, a multivariate regression analysis including all predictors from the CDR will be conducted. The regression coefficients obtained from this model in our sample will be examined to evaluate whether changes in the points given to each predictor in the rule need to be modified in patients with a suspected recurrent VTE.

Minor adjustments

For each existing CDR, a multivariate regression analysis including all predictors from the CDR will be performed. Candidate predictors will also be included in the analysis, but keeping in the model predictors from the CDR. Should one or two candidate predictors significantly improve risk stratification, a modified score could be proposed for patients with suspected recurrent VTE. Potential improvements in classification will be assessed using the Net Reclassification Improvement and the Integrated Discrimination Improvement indices.

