9.5.2 Derivation of a new CDR

Univariate Analysis

Univariate analysis will be used to assess the association between each variable and VTE recurrence. This process will aid selection of the best variables for the multivariate analysis. The appropriate univariate technique will be chosen according to the type of data.

Multivariate Analysis

Multivariate analysis will derive one model to predict recurrent VTE. Those variables found to be strongly associated with the outcome measure ($P<0.05$), by the univariate analysis and have good inter-observer reliability ($\kappa >0.6$), will be combined using logistic regression. For continuous and ordinal variables various cut-points will be examined to determine the optimal cut-point(s). The derived CDR must be easy to use by clinicians and therefore should contain as few variables as possible. Thus, only the most informative variables will be kept in the final model. Points for the score will be attributed according to regression coefficients. The CDR will be presented in clear narrative form that does not require computation or use of statistical aids. Discrimination and calibration of the new CDR will be estimated and compared to those obtained with existed/modified CDRs using the same indices as described above.

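### The sample size assumes 10 predictors per rule, but the derivation screens an uncapped list of up to 94, giving about 1 to 2 events per predictor studied instead of 5-10

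*Combined protocol and SAP*

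**What the plan says.** Section 9.2 (Sample Size Calculation) adopts the criterion that "5-10 patients per predictor studied are required in the smallest outcome category". It then sets the number of predictors for the DVT rule: "We would like to be able to use up to 10 predictors for patients with suspected DVT with a history of VTE". The same allowance is made for a second rule in suspected PE. From this it derives a need for "100 participants with a confirmed recurrent DVT and 100 participants with confirmed recurrent PE". It leaves open whether one rule or two will result.

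Section 6.2.1 points to the predictors to be collected with the words "For a complete list of clinical predictors, refer to" Appendix D.

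Section 9.5.2 (Derivation of a new CDR) begins: "Univariate analysis will be used to assess the association between each variable and VTE recurrence". Variables with P<0.05 and kappa above 0.6 go into a logistic regression, and several cut-points are tried for continuous and ordinal variables. The section asks for a short final rule but gives no number, either for the candidates or for the final model. It mentions no internal validation.

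Section 9.5.1 also adds candidates to the existing rules: "Candidate predictors will also be included in the analysis, but keeping in the model predictors from the CDR". It does not say which candidates.

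**The concern.** The criterion in section 9.2 counts predictors *studied*. If a large list is tested against the outcome and the best few are kept, the number studied is the size of the large list. Choosing by P-value in the same patients uses up the same events as fitting the variables would. A final model of 10 variables chosen this way does not have the stability of 10 variables named in advance.

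The derivation is a secondary objective, but it is the only basis given for N = 745, and the protocol's statement of significance rests on the new rule. Section 9.5.2 will compare the new rule's discrimination and calibration with those of existing rules. The published scores are fixed in advance and carry no selection optimism from this sample; the new rule would. The comparison would then favour the new rule for a reason unrelated to its merit. Section 9.5.3 applies the same tools to estimate in whom imaging might be withheld, so poor calibration would carry through to that estimate.

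**Working it through.** **1. The plan's own figure.** Inputs from section 9.2: 10 predictors per rule, 10 events per predictor (the upper end of 5-10), and confirmation rates of 29% for DVT ("29% of the participants with a suspected recurrent DVT had their recurrence confirmed") and 25% for PE.
- Events per rule = 10 × 10 = 100.
- Suspected DVT: 100/0.29 = 344.8, rounded up to 345. Suspected PE: 100/0.25 = 400. Total 745.

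The figure reproduces exactly.

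**2. Candidates.** Appendix D, counted line by line: presenting history 26, risk factors 15, previous event 14, physical examination 25, ECG 2, chest x-ray 3, laboratory 5, physician impression 3, patient impression 1. Total 94. Several entries contain two or more time windows, which adds parameters.

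**3. Events per predictor studied** = events / candidates screened.
- Two rules, 94 candidates each: 100/94 = 1.06.
- One pooled rule: 200/94 = 2.13.
- Two rules, if only 50 entries apply to each presentation (an assumption): 100/50 = 2.0.

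**4. What the criterion would allow or need.**
- 100 events support 100/10 = 10 to 100/5 = 20 candidates per rule.
- 94 candidates need 94 × 5 = 470 to 94 × 10 = 940 events per rule.
- At 470 events, N = 1,621 + 1,880 = 3,501. At 940 events, N = 3,242 + 3,760 = 7,002.

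**5. Chance selection.** If all 94 were unrelated to the outcome, 94 × 0.05 = 4.7 would be expected to pass P<0.05, before any cut-point search.

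**6. Illustration by simulation.** Assumptions, none from trial data: independent binary candidates with prevalence 5-40%, 8 truly predictive with odds ratio 2, no kappa filter, no cut-point search, validation in 8,000 new patients.

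| Patients and event rate | Approach | c in new patients | Calibration slope |
|---|---|---|---|
| 345 at 29% | screen 94 | about 0.63 | about 0.45 |
| 400 at 25% | screen 94 | about 0.63 | about 0.48 |
| 345 at 29% | screen 50 | about 0.64 | about 0.57 |
| 745 at 27% | screen 94, one pooled model | about 0.67 | about 0.69 |
| 345 at 29% | pre-listed 10, 6 true | about 0.66 | about 0.75 |
| 345 at 29% | pre-listed 10, 4 true | about 0.62 | about 0.65 |
| 345 at 29% | pre-listed 10, 3 true | about 0.60 | about 0.58 |

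In the first row the apparent c is about 0.75, so optimism is about 0.75 − 0.63 = 0.12. The screen keeps about nine variables, of which about 4.4 are noise. The resulting model would look consistent with the allowance of 10.

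**The case against.** **The 10 may mean variables in the final model.** This is the best defence of section 9.2. It does not stand against the section's own wording, which counts predictors studied, nor against the fact that outcome-based selection spends events. The kappa filter removes unreliable variables, not chance associations.

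**A ratio of 1 is the worst case.** This stands in part. It needs two rules that each screen all 94 entries, whereas section 9.5.2 speaks of one model. Section 9.5.2 does not cite Appendix D; that all of it is screened is a reasonable inference from section 6.2.1, not a stated fact. Some entries concern only the leg or only the chest, some are near-duplicates, and inpatient/outpatient status is fixed by eligibility. Hence the range of about 1 to 2, all of it below 5.

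**A pre-listed 10 is not always better.** This stands for discrimination. At 345 patients the gain in c disappears when about 4 of the 8 true predictors are on the list and reverses at 3. For one pooled model there is no gain even with 6 (0.664 against 0.668 for screening). At 94 candidates the calibration advantage persists throughout; at 50, a list with 3 true predictors has about the same slope as screening. Section 2.2.3 itself describes its retrospective source as limited.

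**The Wells DVT model in section 9.5.1.** A reader might infer that this model, with 10 items before any candidate is added, already exceeds the criterion. The documents do not support this. A modified score adding one or two candidates has at most 12 terms, and 100/12 = 8.3 lies within 5-10. How many candidates are tried to find those one or two is a separate question, answered by the same fix.

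**Conclusion.** The concern holds for the derivation of the new rule. The stated 5-10 events per predictor is not a property of the planned analysis; the figure is about 1 for two rules, and about 2 for one pooled rule or for about 50 relevant entries. This rests on a count of Appendix D and on the absence of any step that shortens the list before outcomes are used.

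The size of the harm rests on the simulation's assumptions and is an illustration. Correlated predictors, the kappa filter and the cut-point search would all change the figures. The direction, an optimistic apparent c and a calibration slope well below 1, appears in every screening scenario examined.

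A reader might infer that the whole study is undersized. The documents do not support that: the primary analysis in section 9.5 validates published rules and selects no predictors, so this point leaves it untouched. Nor does it follow that more patients are required, since the analysis can be brought into line with the events already planned.

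**What to change.** In section 9.2, restate events per predictor for the candidates that will actually be screened, for one rule and for two.

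In section 9.5.2, before outcome data are analysed, choose one of two routes:
- Freeze a list of 10-20 candidate parameters per rule, drawn from the literature, expert survey and retrospective cohort in section 2.2. Count every category and cut-point as a parameter, and label the other Appendix D items exploratory.
- Keep the wider list, and replace the unpenalised P<0.05 screen with a penalised or shrunken model.

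Under either route, bootstrap the whole selection process, including cut-point choice, and use the optimism-corrected c and slope when comparing the new rule with existing ones. The corrected slope can also serve as a shrinkage factor, which addresses calibration though not lost discrimination. Name the candidates for section 9.5.1 in the same way.

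The cost is SAP wording and a steering committee decision, with no extra patients or data. With a frozen list, a predictor outside it cannot enter the main rule. With the wider list, the protocol must state a less favourable ratio.
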